21.1.1 Acronyms

Acronym	Term			
ACE	Angiotensin Converting Enzyme			
ACS	Acute Coronary Syndrome			
ADE / SADE	Adverse Device/Drug Effect / Serious Adverse Device/Drug Effect			
AE / SAE	Adverse Event / Serious Adverse Event			
ARB	Angiotensin Receptor Blocker			
ASADE / USADE	Anticipated Serious Adverse Device Effect / Unanticipated Serious Adverse Device Effect			
BMS	Bare Metal Stent			
CABG	Coronary Artery Bypass Graft			
CAD	Coronary Artery Disease			
CAPA	Corrective and Preventative Action			
CEC	Clinical Events Committee			
СК	Creatine Kinase			
CK-MB	Creatine Kinase Muscle-Brain Isoenzyme			
CoCr	Cobalt Chromium			
CRF / eCRF	Case Report Form / electronic Case Report Form			
cTn	Cardiac troponin			
СТО	Chronic Total Occlusion			
DAPT	Dual Antiplatelet Therapy			
DSMB	Data Safety Monitoring Board			
ECG	Electrocardiogram			
EDC	Electronic Data Capture			
EES	Everolimus-eluting Stent			
FAS	Full Analysis Set			
FDA	Food and Drug Administration			
FFR	Fractional Flow Reserve			
IB	Investigator's Brochure			
IFU	Instructions for Use			
IRB	Institutional Review Board			
IVUS	Intravascular Ultrasound			

Acronym	Term
LAD	Left Anterior Descending Artery
LCX	Left Circumflex
LVEF	Left Ventricular Ejection Fraction
MACE	Major Adverse Cardiac Events
MI	Myocardial Infarction
MLD	Minimum Luminal Diameter
mTOR	Mammalian Target of Rapamycin
NIH	Neointimal Hyperplasia (IVUS)
NSTEMI	Non ST Elevation Myocardial Infarction
PBMA	poly n-butyl methacrylate
PCI	Percutaneous Coronary Intervention
PMA	Premarket Approval
PP	Per Protocol Analysis Dataset
PTCA	Percutaneous Transluminal Coronary Angioplasty
QCA	Quantitative Coronary Angiography
RCA	Right Coronary Artery
RES	Ridaforolimus-eluting Stent
RVD	Reference Vessel Diameter
SAE	Serious Adverse Event
SAP	Statistical Analysis Plan
STEMI	ST Elevation Myocardial Infarction
TLF	Target Lesion Failure
TLR	Target Lesion Revascularization
TVF	Target Vessel Failure
TVR	Target Vessel Revascularization
USADE	Unanticipated Serious Adverse Device/Drug Effect
ZES	Zotarolimus-eluting Stent

Abbreviation	Term	
ACC / AHA / SCAI	American College of Cardiology / American Heart Association / Society for Cardiovascular Angiography and Interventions (dual anti- platelet therapy guideline)	
ARC	Academic Research Consortium (definitions for bleeding, death, myocardial infarction, and stent thrombosis)	
BARC	Bleeding Academic Research Consortium (BARC) (classification for bleeding)	
CCS	Canadian Cardiovascular Society (angina grading scale)	
HIPAA	Health Insurance Portability and Accountability Act (U.S. privacy rule for protected health information)	
JAAC	Journal of the American College of Cardiology	
JCS	Japanese Circulation Society	
MHLW	Ministry of Health, Labour and Welfare (Japan)	
NHLBI	National Heart, Lung, and Blood Institute (coronary artery dissection scale)	
NYHA	New York Heart Association (heart failure classification)	
TIMI	Thrombolysis In Myocardial Infarction (bleeding definition and coronary artery blood flow scale)	

1. LIST OF ABBREVIATIONS AND DEFINITIONS OF TERMS

ACS	Acute Coronary Syndrome
AE	Adverse Event
ARC	Academic Research Consortium
ATC	Anatomical Therapeutic Chemical
BMI	Body Mass Index
CABG	Coronary Artery Bypass Graft
Ccr	Calculated creatinine clearance
CEC	Clinical Events Committee
CI	Confidence Interval
CK	Creatine Kinase
CK-MB	Creatine Kinase Muscle-Brain Isoenzyme
CRF	Cardiovascular Research Foundation
DAPT	Dual Antiplatelet Therapy
DS	Diameter Stenosis
ECG	Electrocardiogram
eCRF	electronic Case Report Form
FFR	Fractional Flow Reserve
FAS	Full Analysis Set
IS	Interpolated Reference Vessel Diameter
LAD	Left Anterior Descending Artery
LVEF	Left Ventricular Ejection Fraction
MACE	Major Adverse Cardiac Event
MedDRA	Medical Dictionary for Regulatory Activities
MI	Myocardial Infarction
MIN	In Stent Minimum Lumen Diameter
PCI	Percutaneous Coronary Intervention
PPS	Per Protocol Set
PT	Preferred Term
QCA	Quantitative Coronary Angiography
SAE	Serious Adverse Event
SAF	Safety Analysis Set
SAP	Statistical Analysis Plan
SAS	Statistical Analysis System
SOC	System Organ Class
STEMI	ST Elevation Myocardial Infarction
TIMI	Thrombolysis In Myocardial Infarction
TLF	Target Lesion Failure
TLR	Target Lesion Revascularization
TVF	Target Vessel Failure
TVR	Target Vessel Revascularization
ULN	Upper Limit of Normal
USADE	Unanticipated Serious Adverse Device Event

T:\PROJ\Medinol\CXA27472\06 Biostatistics\Documentation\SAP\Final Document:

1.0 08Aug2018\JNIR01_SAP_Final V1.0_08Aug2018.docx

[name] Version Number: Author: Final V1.0 Version Date: 08Aug2018

Template No: CS_TP_BS016 Revision 4 Reference: CS_WI_BS005

Effective Date: 01Apr2016

Copyright © 2009, 2010, 2012, 2016 Quintiles Transnational Corp. All rights reserved. The contents of this document are confidential and proprietary to Quintiles Transnational Corp. Unauthorized use, disclosure or reproduction is strictly prohibited.

WHODD WHO Drug Dictionary

Document: T:\PROJ\Medinol\CXA27472\06_Biostatistics\Documentation\SAP\Final

1.0_08Aug2018\JNIR01_SAP_Final V1.0_08Aug2018.docx

Author: [name] Version Number: Final V1.0 Version Date: 08Aug2018

Template No: CS_TP_BS016 Revision 4 Reference: CS_WI_BS005

2. Introduction

This document describes the rules and conventions to be used in the presentation and analysis of efficacy and safety data for Protocol JNIR01. It describes the data to be summarized and analyzed, including specifics of the statistical analyses to be performed.

This statistical analysis plan (SAP) is based on protocol version 2.0, dated September 18, 2016.

3. STUDY OBJECTIVES

The objective of this clinical trial is to evaluate MedJ-01 safety and efficacy for de novo or restenosis lesion with target vessel diameter of 2.5 mm to 4.25 mm, for patients undergoing coronary artery stent implantation.

4. STUDY DESIGN

4.1. GENERAL DESCRIPTION

This is a prospective, multi-center, single-arm, open label clinical trial. Lesions planned to be treated must be declared and recorded at time of enrollment.

The JNIR01 Trial will enroll approximately 100 patients with a wide spectrum of Percutaneous Coronary Intervention (PCI) indications (stable angina as well as Acute Coronary Syndrome (ACS), including subacute STEMI (>72 hours since first hospital presentation).

Clinical follow-up will be performed at 30 days, 6 months, and 1, 2, 3, 4, and 5 years post enrollment.

Adjudication of study endpoints will be determined by an independent clinical events committee (CEC). The CEC will be responsible for the adjudication of the clinical trial endpoint events as well as all deaths that occur throughout the trial and device non-success.

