6.4.7 Treatment Failures and Device Malfunctions of the MedJ-01

In case of failure to deliver a study stent, typical measures should be undertaken to ensure the lesion has been adequately prepared, such as use of appropriately sized pre-dilatation balloons, cutting or scoring balloons, and/or rotational atherectomy (including DCA) as appropriate. Guide

catheter support should be optimized using standardized techniques, including use of buddy wires and/or guide extension devices as appropriate. If the study stent can still not be delivered, any commercially available stent may be used to successfully and safely complete the procedure.

All failures and MedJ-01 malfunctions will be documented on the appropriate CRF. The MedJ-01 should be returned to Medinol for analysis and be reported in the clinical results. Instructions for returning the MedJ-01 are included in the trial's Site Binder. Treatment failures or device malfunctions should be reported in the CRF within 24 hours, per the instructions of EDC completion.

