8.4 Other Aspects of Clinical Quality Assurance

8.4.1 Clinical Events Committee

The Clinical Events Committee (CEC) will be comprised of cardiologists who are not participants in the trial and who have no conflict of interest with the trial or the trial sponsor. All members of the CEC will be blinded to the primary results of the trial.

The CEC will be responsible for the adjudication of the clinical trial endpoint events. At the onset of the trial, the CEC will establish explicit rules outlining the process for adjudication and the algorithms followed in order to classify a clinical endpoint event. The CEC will also review and rule on all deaths that occur throughout the trial. In addition, the CEC will review and adjudicate device non-success. Definitions are provided in Section 21.1.

Once the specific criteria for clinical endpoints are established by the CEC, Cardiovascular Research Foundation will be responsible for preparing all clinical endpoint event dossiers and for the conduct of the CEC meetings.

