21 DEFINITIONS AND ACRONYMS

21.1 Definitions

ABRUPT CLOSURE

- Abrupt closure is defined as the occurrence of new (during the baseline procedure) severely reduced flow (TIMI grade 0-1) within the target vessel that persisted and required rescue by stenting or other treatment, or resulted in myocardial infarction or death. Abrupt closure requires proven association with a mechanical dissection of the treatment site or instrumented vessel, coronary thrombus, or severe spasm. Abrupt closure does not connote "no reflow" due to microvascular flow limitation, in which the epicardial artery is paten but had reduced flow. Abrupt closure also does not connote transient closure with reduced flow in which the baseline treatment application reverses the closure.
- Sub-abrupt closure is defined as abrupt closure that occurred after the baseline procedure is completed and the patient left the catheterization laboratory and before the 30-day follow-up evaluation.
- Threatened abrupt closure is defined as a grade B dissection and ≥50% diameter stenosis or any dissection of grade C or higher.

ACUTE CORONARY SYNDROME

Acute coronary syndrome (ACS) refers to a spectrum of clinical presentations ranging from those for ST-segment elevation myocardial infarction (STEMI) to presentations found in non–ST-segment elevation myocardial infarction (NSTEMI) or in unstable angina. For the purpose of this CIP, ACS will be defined as hospitalization for angina pain or discomfort within the previous 24 hours to their hospitalization with any one (or more) of the following criteria:

- Elevated troponin or creatine kinase-MB (CK-MB) consistent with MI, as reported by local laboratory and measured prior to baseline PCI
- Electrocardiographic changes (including transient changes) comprising new or presumably new ST segment depression ≥ 0.1 mV (≥ 1 mm), or ST segment elevation ≥ 0.1 mV (≥ 1 mm) in at least 2 contiguous leads, or new or presumably new Left Bundle Branch Block

ACUTE SUCCESS

Acute Success is classified according to the following definitions:

• Device Success

Device success is defined as achievement of a final in-stent residual diameter stenosis of <50% (by QCA), using the assigned device only and without a device malfunction.

Lesion Success

Lesion success is defined as achievement of a final in-stent residual diameter stenosis of <50% (by QCA) using any percutaneous method.

Procedure Success

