15.2.1. SECONDARY EFFICACY VARIABLES & DERIVATIONS

15.2.1.1. Device, Lesion, and Procedure Success at Time of Baseline Procedure

 Device success is defined as achievement of a final in-stent residual diameter stenosis of <50% by Quantitative Coronary Angiography (QCA) in the target lesion, using the assigned device only and without a device malfunction. Device malfunctions are defined as occurring during the time of use.
 From final procedure QCA, Residual Diameter Stenosis (DS):

DS = 100*(1-mean (MIN1, MIN2) / mean (IS1, IS2)

Where 1 refers to projection = Projection 1

2 refers to projection = Projection 2

MIN: In stent minimum lumen diameter

IS: interpolated reference vessel diameter

If DS <50% and no device malfunction then Device Success = 1

Else if DS>=50% then Device Success = 0.

 Lesion success is defined as achievement of a final in-stent residual diameter stenosis of <50% (by QCA) in the target lesion using any percutaneous method.

From final procedure QCA, Residual Diameter Stenosis (DS) is calculated using the formula given above and:

If DS <50% then Lesion Success = 1

Else if DS \geq 50% then Lesion Success = 0.

Procedure success is defined as achievement of a final in-stent diameter stenosis of <50% (by QCA) using the assigned device and/or with any adjunctive devices, without the occurrence of cardiac death, Q wave or non-Q wave MI, or repeat revascularization of the target lesion during the hospital stay. Each Event is defined from adjudication, with peri-procedural MIs adjudicated per SCAI [2] definition.

The analysis of device success and lesion success will be performed on lesion level, i.e., the numerator will be the number of target lesions meeting the criteria for device or lesion success, respectively, and the denominator will be the total number of target lesions.

The analysis of procedure success will be performed on patient level, i.e., the numerator will be the number of patients with all target lesions meeting the criteria for procedure success and the denominator will be the total number of patients.

These analyses will be performed by Cardiovascular Research Foundation.

Document: T:\PROJ\Medinol\CXA27472\06 Biostatistics\Documentation\SAP\Final

1.0_08Aug2018\JNIR01_SAP_Final V1.0_08Aug2018.docx

Author: [name] Version Number: Final V1.0 Version Date: 08Aug2018

Template No: CS TP BS016 Revision 4 Reference: CS WI BS005

Effective Date: 01Apr2016

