15.2.1.2. Clinical secondary endpoints defined from CEC adjudication data

The following secondary clinical endpoints as adjudicated by the CEC will be evaluated at 30 days, 6 months, and 1, 2, 3, 4, and 5 years, except as noted:

- TLF at 30 days, 6 months, and 2, 3, 4 and 5 years defined as the composite of cardiac death, target vessel related MI, or clinically-driven TLR.
- Major adverse cardiac events (MACE; the composite rate of cardiac death, any MI or clinically-driven TLR)
- Target vessel failure (TVF; the composite rate of all-cause death, target vessel related MI or clinicallydriven TVR)
- All-cause mortality
- Cardiac death
- Myocardial infarction
- · Target vessel related MI
- Clinically-driven TLR: TLR is defined as any repeat percutaneous intervention of the target lesion or bypass surgery of the target vessel (i.e. revascularization) performed for clinically driven restenosis or other complication of the target lesion.
- Clinically-driven TVR: TVR is defined as any repeat percutaneous intervention or surgical bypass of any segment of the target vessel (i.e. revascularization) performed for clinical driven restenosis.
- Stent thrombosis: Stent thrombosis is defined according to timing, type, and degree of certainty per ARC definition (Table A:). Stent thrombosis should be reported as a cumulative value at the different time points and with the different separate time points. Time 0 is defined as the time point after the guiding catheter has been removed and the patient left the catheterization lab after the baseline procedure. Stent thrombosis will also be reported by ARC category and, in particular, for ARC categories definite and probable.

Table A: ARC Definition of Stent Thrombosis

Timing	Acute	≤ 24 hours post stent implantation
	Subacute	> 24 hours to 30 days post stent implantation
	Late	> 30 days to 1 year post stent implantation
	Very late	> 1 year post stent implantation
Туре	Primary	Occurs in target lesion or margins after baseline procedure
	Secondary	Occurs after revascularization (TLR, TVR, or non-TVR)

Document: T:\PROJ\Medinol\CXA27472\06 Biostatistics\Documentation\SAP\Final

1.0_08Aug2018\JNIR01_SAP_Final V1.0_08Aug2018.docx

Author: [name] Version Number: Final V1.0 Version Date: 08Aug2018

Template No: CS TP BS016 Revision 4 Reference: CS WI BS005

Effective Date: 01Apr2016

Copyright © 2000, 2010, 2012, 2016 Quip

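### The SAP's device-success derivation leaves out the CEC decision and part of its own definition, so a device failure with residual stenosis below 50% can be counted as a success or left uncoded

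*SAP*

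**What the plan says.** Both documents give this decision to the CEC. SAP 4.1 describes the remit as endpoint events "as well as all deaths that occur throughout the trial and device non-success". Protocol 8.4.1 states: "In addition, the CEC will review and adjudicate device non-success", and refers to Section 21.1 for definitions.

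Protocol 21.1 defines device success as a final in-stent residual diameter stenosis (DS) below 50% by QCA, "using the assigned device only and without a device malfunction". SAP 15.2.1.1 repeats that definition in prose and then gives two code lines: "If DS <50% and no device malfunction then Device Success = 1" and "Else if DS>=50% then Device Success = 0". On malfunctions it adds only this: "Device malfunctions are defined as occurring during the time of use". It names no form, dataset or committee as the source.

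The same SAP section uses adjudication for the clinical events within procedure success. The next section, headed "Clinical secondary endpoints defined from CEC adjudication data", does not list device success. SAP 4.3, which records changes from the protocol, is silent on the matter.

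On data capture, Protocol 6.4.7 says: "All failures and MedJ-01 malfunctions will be documented on the appropriate CRF". The same section lets the operator finish with any marketed stent if the study stent cannot be delivered.

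**The concern.** Device success is a listed secondary endpoint. SAP 15.2.2 reports it with an exact 95% interval and a difference between JNIR and BIONICS. The trial is open label, and the planned CEC review is the independent check on what counts as a device failure. If the reported rate does not draw on that review, and the code is looser than the definition, some device failures may not appear as failures. The rate is likely to be close to 100%, so one or two lesions decide whether the table shows any failures at all.

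**Working it through.** The plan states no figure for this endpoint, so there is none to reproduce. The check has two parts.

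**1. Definition against code.** Inputs: the definition in Protocol 21.1 (repeated in SAP 15.2.1.1) and the two code lines in SAP 15.2.1.1.

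| Final DS | Malfunction | Assigned device only | Definition gives | Code gives |
|---|---|---|---|---|
| <50% | no | yes | 1 | 1 |
| <50% | no | no | 0 | **1** |
| <50% | yes | yes or no | 0 | **no value** |
| ≥50% | either | either | 0 | 0 |

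The code departs from the definition in the second and third rows. A CEC decision of non-success would correct both, but no CEC variable enters the code.

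Both rows can occur. Protocol 6.4.7 allows a commercial stent after failed delivery. SAP 6.2 de-registers only patients in whom the stent could not be implanted for reasons unrelated to the device, so device-related delivery failures stay in the FAS. Whether a failed delivery sets the malfunction flag is not stated: Protocol 6.4.7 names failures and malfunctions separately, while Protocol Table 11 lists failed delivery as a device deficiency. If the flag is not set, the lesion falls in row two and is coded 1. If it is set, the lesion falls in row three and has no code.

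The handling of an uncoded lesion is also unsettled. SAP 15.2.1.1 takes all target lesions as the denominator, which would in effect count it as a failure. SAP 7.1 removes missing values from percentage denominators, which would drop it.

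**2. Scale.** Inputs: in the PIONIR study of the bare-metal platform (Protocol 3.3.1), lesion success was 280/280 and device success 275/280. With the same 280 cases in both, all 280 − 275 = 5 device failures met lesion success. QCA stenosis alone would not have identified them.

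- Assumed failure rate for MedJ-01: 5/280 = 1.8%.
- Assumed number of target lesions, since the documents give none: 100 to 150.
- Expected failures: 100 × 5/280 = 1.8; 150 × 5/280 = 2.7.
- Chance of at least one, 1 − (1 − 5/280)^L: 83.5% for L = 100; 93.3% for L = 150.
- Weight of one lesion: 1/150 = 0.7 points to 1/100 = 1.0 point.

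Illustration with 120 lesions and two true device failures, both with DS below 50% (exact Clopper-Pearson 95% intervals):

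| Handling | Rate | 95% interval |
|---|---|---|
| Both coded 0 | 118/120 = 98.3% | 94.1 to 99.8 |
| One coded 1, one coded 0 | 119/120 = 99.2% | 95.4 to 100.0 |
| Both coded 1 | 120/120 = 100% | 97.0 to 100 |
| Both dropped as missing | 118/118 = 100% | 96.9 to 100 |

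The last lower limit is 0.025^(1/118) = 0.969. With two failures coded 0, the rate is 98.0% (93.0 to 99.8) for 100 lesions and 98.7% (95.3 to 99.8) for 150.

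**The case against.** The best defence is that the SAP is silent here and does not contradict itself. SAP 4.1 states a general rule that the CEC adjudicates study endpoints, and the malfunction flag could be the adjudicated value. The prose above the code lines contains the full definition, including the assigned-device condition, so a careful programmer might apply it. The Cardiovascular Research Foundation prepares the CEC dossiers (Protocol 8.4.1) and also runs this analysis (SAP 15.2.1.1), so the analyst has access to the decisions. If the CEC applies the Section 21.1 definition, it and a correctly coded rule would seldom disagree.

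Part of this stands. A reader might infer that device success rests on what open-label sites choose to tick, and that CEC review changes nothing. The documents do not support that. The source of the flag is unstated rather than shown to be the site's entry, the stenosis component comes from the core laboratory, and the CEC's own adjudication rules are not among the documents.

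The defence does not remove the point. Even an adjudicated malfunction flag would leave row two wrong, because the code line does not test for the assigned device, and row three uncoded. Neither document says which result prevails if the CEC and the code disagree.

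**Conclusion.** The point holds as a defect of specification. Both documents assign device non-success to the CEC; the derivation does not use the decision, does not source the malfunction flag, and departs from its own definition in two situations that the protocol allows.

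The size is about two or three lesions expected, or 0.7 to 1.0 points each. This rests on an assumed 100 to 150 lesions and on a failure rate borrowed from a bare-metal study. The protocol allows up to four target lesions per patient, so 150 is not a ceiling. How many failures would be miscoded cannot be known from the documents, and the intervals in the illustration overlap heavily.

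A reader might also infer that the trial's main conclusion is at risk. It is not: SAP 7.5 and 8.4 make the secondary endpoints descriptive, and device success does not enter target lesion failure.

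**What to change.** Replace the two code lines in SAP 15.2.1.1 with a complete rule for each target lesion:

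- **Device Success = 0** if the CEC adjudicated device non-success, or final DS is ≥50%, or a non-assigned stent was used, or a device malfunction occurred (CEC-adjudicated where available, otherwise as recorded on the eCRF).
- **Device Success = 1** only if DS is <50%, only the assigned device was used, there was no malfunction, and there was no CEC finding of non-success.

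Name the source of the malfunction flag, say whether a failed delivery sets it, and state that the CEC decision prevails. Derive the BIONICS comparator by the same rule; if its data do not allow that, report JNIR alone for this endpoint. If the sponsor does not intend to use the CEC decision, declare that in SAP 4.3 and still correct the two faulty rows.

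The cost is SAP wording and one extra derived variable, since the CEC review is already planned. The reported device-success rate may be slightly less favourable.
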